6.8.2. Allowed Concomitant Therapy and Rescue Therapy

If medically necessary due to intolerable symptoms, rescue therapy will be permitted at the discretion of the investigator based on disease worsening as evaluated by the investigator (ie, increased EASI or BSA), or as reported by the subject (ie, worse itch). Optimized skin care is expected to be followed prior to and maintained throughout the study as per current guidelines and recommendations for AD (eg, avoidance of irritants).

Whenever possible during the Double-Blind Treatment Period, rescue therapies should be withheld for at least 4 weeks from the start of the study treatment. If possible, investigators should attempt to limit initial rescue therapy to topical medications as a first line treatment for AD and AD flares according to current guidelines and recommendations (Eichenfield 2014, Eichenfield 2017). Primarily topical medium potency corticosteroids such as triamcinolone acetonide 0.1% and fluocinolone acetonide 0.025% should be used, and applied to problem areas only, in conjunction with oral antihistamines, if needed. Topical calcineurin inhibitors may also be applied to problem areas if additional therapy is required for intractable symptoms. Only when symptoms continue to persist are systemic corticosteroids or nonsteroidal systemic immunosuppressive drugs (eg, cyclosporine, methotrexate, mycophenolate mofetil, azathioprine) recommended for rescue therapy.

If a subject receives rescue therapy with systemic corticosteroids or non-steroidal systemic immunosuppressive drugs, study treatment will need to be immediately discontinued. After treatment with these medications is completed, study treatment may be resumed if deemed appropriate by the investigator and the medical monitor, but no sooner than 5 half-lives after the last dose of systemic rescue medication.

Rescue therapies and the indication and details (ie, name, dose, frequency of administration, strength, duration of use) will be recorded in the subject's chart and eCRF, if applicable. Investigators should make every attempt to conduct efficacy and safety assessments (eg, disease severity scores, safety labs) immediately before administering any rescue treatment. An unscheduled visit may be used for this purpose, if necessary.

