9.3. Early Study Treatment Termination

Subjects who stop taking their study treatment before the end of the Double-Blind Treatment or Open-Label Extension Periods will return to the study site for an EoT Visit within 1 week of the last study treatment administration. Subjects who stop taking their study treatment before the end of the Double-Blind Treatment Period are not eligible to participate in the Open-Label Extension Period. Visit assessments are detailed in the [REDACTED]. Study site staff will work with subjects who withdraw early to obtain as much follow-up data as possible. Lymphocyte counts should be monitored until returned to approximately baseline or stable. In the Double-Blind Treatment Period, whenever possible, subjects should continue in the study even if study treatment has been discontinued. Subjects who discontinue study treatment, but who consent to remain in the study will continue to comply with study visits and assessments.

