11.4. Missing Data

11.4.1. Primary Methods of Handling Missing Data and Rescue Medication Uses

In order to analyze primary and secondary efficacy endpoints at Week 12 in the Full Analysis Set (FAS), handling missing data and rescue medication uses are specified as following.

For the primary endpoint of percentage change in EASI from Baseline to Week 12, EASI scores after rescue medication use will be set to missing. All missing EASI scores at scheduled visits up to Week 12 will be imputed using a multiple imputation (MI) technique with a fully conditional specification method and predictive mean matching for EASI scores (Heitjan 1991, van Buuren 2007). Detailed MI model descriptions and analysis procedures will be specified in the SAP.

For analysis of dichotomous endpoints (eg, 75% reduction in EASI [EASI-75], vIGA 0 to 1) at Week 12, all subjects in the FAS will be included in the analyses. Subjects in any of the following cases will be considered as “non-responders” or “failure”:

- Use rescue medications during treatment;
- Prematurely discontinue from study due to any reason prior to Week 12; or
- With missing data at Week 12 for any reason.

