The scores from the 7 questions are added up to give an overall POEM score (0-28). An overall POEM score of 0-2 = ‘clear/almost clear’, 3-7 = ‘mild’, 8-16 = ‘moderate’, 17-24 = ‘severe’, and 25-28 = ‘very severe atopic eczema’.

- **DLQI** is a 10-item patient-reported outcome (PRO) measure that assesses the extent to which the skin condition has affected the subject’s quality of life over the past week, including 6 domains (daily activities, personal relationships, symptoms and feelings, leisure, work/school, and treatment). Total score (0-30) will be calculated as the sum of 10 questions with each ranging from 0 to 3. The scoring of each answer is as follows:

Very much	Scored 3
A lot	Scored 2
A little	Scored 1
Not at all	Scored 0
Not relevant	Scored 0
Question unanswered	Scored 0

Question 7	Question 7A	Score
Yes	Any response	3
No	A lot	2
No	A little	1
No	Not at all	0
Not relevant	Any response	0

[figure not shown]
If one question is left unanswered this is scored 0 and the scores are summed and expressed as usual out of a maximum of 30. If two or more questions are left unanswered the total DLQI score is missing. If question 7 is answered ‘yes’ or ‘not relevant’, then the answer of 7a will be ignored.

B. Primary Efficacy Outcome Analysis

The primary endpoint of percentage change in EASI from Baseline to Week 12 will be analyzed based on the FAS using an analysis of covariance (ANCOVA) model. The ANCOVA model will include treatment group as factors, Baseline EASI score and the two randomization factors of baseline vIGA (3 versus 4) and

region [REDACTED] as covariates. EASI scores after rescue medication use will be set to missing. All missing EASI scores at scheduled visits up to Week 12 will be imputed using a multiple imputation (MI) technique with a fully conditional specification (FCS) method and predictive mean matching (PMM) for EASI scores (Heitjan 1991, van Buuren 2007). The rescue medications considered for the purposes of efficacy analysis will include topical and systemic corticosteroids used during the DB Treatment Period of the study.

For MI, 100 imputation models will be generated, including treatment, baseline vIGA (3 versus 4), region [REDACTED] baseline EASI score, and EASI scores at the previous scheduled visits. Percent change in EASI at Week 12 will be derived from the imputed EASI values.

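### The SAP's rescue flag for efficacy names only corticosteroids, while the protocol's rescue list is wider; the difference is undeclared and no planned analysis applies the wider rule

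*SAP*

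**What the plan says.** **Rescue drugs.** Protocol 6.8.2 describes steps. Topical corticosteroids come first, "in conjunction with oral antihistamines, if needed". Next, "Topical calcineurin inhibitors may also be applied to problem areas if additional therapy is required for intractable symptoms". If symptoms persist, the section has "systemic corticosteroids or nonsteroidal systemic immunosuppressive drugs (eg, cyclosporine, methotrexate, mycophenolate mofetil, azathioprine) recommended for rescue therapy".

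**After systemic rescue.** The same section states: "If a subject receives rescue therapy with systemic corticosteroids or non-steroidal systemic immunosuppressive drugs, study treatment will need to be immediately discontinued". Later resumption is possible. Protocol 9.3 keeps such subjects under observation: "Subjects who discontinue study treatment, but who consent to remain in the study will continue to comply with study visits and assessments".

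**Analysis rule in the protocol.** Section 11.4.1 states: "For the primary endpoint of percentage change in EASI from Baseline to Week 12, EASI scores after rescue medication use will be set to missing". For dichotomous endpoints, its first trigger for non-response is "Use rescue medications during treatment". Neither rule is limited by drug class.

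**Analysis rule in the SAP.** Section 8.B keeps the set-to-missing rule and then defines rescue: "The rescue medications considered for the purposes of efficacy analysis will include topical and systemic corticosteroids used during the DB Treatment Period". This is the SAP's only definition of rescue for efficacy. Section 8.C applies non-responder imputation (NRI) after rescue, and Section 8.D does the same for EASI-50, EASI-90 and the peak NRS response.

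**Declared changes.** SAP Section 11 has two entries, the pairwise correlations and the COVID-19 changes.

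**The concern.** The primary endpoint, both key secondary endpoints and the NRI-based secondary endpoints all depend on which drugs trigger the rescue rule. Under the SAP wording, the same clinical event is a failure or an ordinary observation according to drug class. A subject rescued with a topical calcineurin inhibitor alone, or with cyclosporine, would keep the observed Week 12 EASI in the primary analysis and could be counted as a responder. So would any EASI value recorded between such use and a later corticosteroid. After a systemic immunosuppressant the retained values would be taken off study drug, unless it had been resumed. They would then partly reflect the rescue agent rather than the randomized treatment.

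The study is an exploratory Phase 2 trial without a formal testing strategy, so Type I error is not the issue. What is at stake is whether the estimates follow the protocol's rule, and whether a reader can tell that they do not.

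**Working it through.** **1. The two lists side by side**

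| Class | Protocol 6.8.2 | SAP 8.B efficacy flag |
|---|---|---|
| Topical corticosteroids | rescue | named |
| Oral antihistamines | adjunct to topical rescue | not named |
| Topical calcineurin inhibitors | rescue | not named |
| Systemic corticosteroids | rescue | named |
| Nonsteroidal systemic immunosuppressants | rescue | not named |

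**2. Does another rule catch these subjects?** The second non-response trigger in Protocol 11.4.1 is leaving the study before Week 12, not stopping study drug. A subject taken off study drug after systemic rescue who attends Week 12 does not meet it. The third trigger, missing Week 12 data, does not apply either.

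**3. Does another planned analysis apply the wider rule?**
- Multiple imputation (MI) in the FAS and mFAS, NRI, LOCF and WCCF all use the 8.B flag.
- The tipping-point analysis shifts imputed values only, so an unflagged post-rescue score is never stressed.
- The observed-case analyses (mFAS, PPS, TCS) disregard rescue.
- PPS and TCS may drop some of these subjects, but they remove whole subjects and do not censor after rescue.
- The post hoc analyses in SAP Section 12 reuse the Section 8 methods or use observed cases.

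**4. The plan's own design figures.** Inputs from Protocol 11.2: difference 35 points, SD 41, 1-sided alpha 0.025, power at least 90%, dropout up to 25%, 40 per arm. A two-sample t-test (noncentral t) needs 30 evaluable subjects per arm, with power 90.2%, and 30/(1 − 0.25) = 40. The planned size is reproduced and is not in dispute. It supplies n = 40 and SD = 41 below.

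**5. Responder endpoints.** One unflagged responder changes an arm's rate by 1/40 = 2.5 percentage points; 2 or 4 such subjects change it by 5.0 or 10.0. The SE of a difference is √(2p(1−p)/40), with p assumed equal in both arms:

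| Assumed p | SE (points) | 2.5/SE |
|---|---|---|
| 0.10 | 6.7 | 0.37 |
| 0.20 | 8.9 | 0.28 |
| 0.40 | 11.0 | 0.23 |

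**6. Primary endpoint.** Under the protocol's rule the value would be imputed, so one subject changes the arm mean by (observed − imputed)/40. This ignores any further effect of the retained value on other subjects' imputations. The planned SE of a difference is 41 × √(2/40) = 9.17 points.

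| Assumed gap | Points | Change in arm mean | Subjects for one SE |
|---|---|---|---|
| 0.5 SD | 20.5 | 0.51 | 9.17/0.51 = 17.9 |
| 1 SD | 41 | 1.03 | 9.17/1.03 = 8.9 |
| 2 SD | 82 | 2.05 | 9.17/2.05 = 4.5 |

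The counts are net: subjects in one arm beyond those in the other, with gaps in the same direction.

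**The case against.** **The SAP's verb is inclusive.** It says the rescue drugs will include corticosteroids, not that they are limited to them. That is a possible reading, but no other SAP text adds a class. If the list is open, the flag behind the primary endpoint is undefined and cannot be reproduced. Either reading calls for a correction to the same sentence.

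**The protocol leaves detail to the SAP.** Its synopsis says rescue handling will be described in both documents, and Section 6.8.2 is management guidance rather than an analysis code list. But Section 11.4.1 then states the rule itself and defers only the MI model and analysis procedures. Even a permitted narrowing is a change that Section 11 should record. The point does stand for oral antihistamines: Section 6.8.2 pairs them with topical rescue, while Protocol Section 5 lists them in the usual skin-care routine. Their status has to be stated, because the protocol does not settle it.

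**Few subjects will be affected.** A subject who follows the 6.8.2 sequence uses a corticosteroid before any unlisted class and is already flagged. This stands as a limit on size, and the documents do not show that any unflagged subject exists. The topical-corticosteroid-first order is, however, advisory.

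**Some traceability exists.** SAP 9.B plans a rescue listing that is not restricted to corticosteroids, so unlisted classes should be visible there if captured. A listing does not give counts by arm or estimates under the wider rule.

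**Conclusion.** The concern holds. Followed literally, SAP 8.B departs from the protocol's rescue rule for the primary, key secondary and NRI-based secondary endpoints, and the departure is neither declared nor examined in any planned analysis. The wider rule comes from reading Protocol 11.4.1 together with 6.8.2, since 11.4.1 carries no drug list of its own.

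The effect on the primary endpoint is small unless several subjects are affected. It is larger per subject for the responder endpoints, at roughly a quarter to a third of a standard error each. These sizes rest on 40 per arm, the planned SD, and the assumed response rates and gaps shown in the working. The direction of bias cannot be derived from the documents. This should be fixed, as a matter of traceability and robustness; it does not threaten the design.

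**What to change.** **If treatment codes are still blinded:** align the rescue flag in SAP 8.B with the atopic dermatitis rescue classes in Protocol 6.8.2, state whether oral antihistamines count, and apply one flag to MI, NRI, LOCF and WCCF.

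**If the data are already unblinded,** as the post hoc analysis set in SAP 5.G and the content of SAP Section 12 suggest: leave the primary flag unchanged and declare the narrowing in SAP Section 11. Add a labelled sensitivity analysis of the primary and key secondary endpoints under the protocol's wider rescue definition, with the status of antihistamines stated. SAP Section 1 already provides for labelled ad hoc analyses after unblinding.

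**In either case,** report by arm the number of subjects whose first or sole rescue was an unlisted class.

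The cost is a longer medication code list, one Section 11 entry and one rerun of existing programs. First check that the eCRF captures every class, because Protocol 6.8.2 requires eCRF entry only where applicable. The downside is slightly more missing or non-response values. Only the analysis flag changes; patient management does not.

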Multiple results of ANCOVA (least square [LS] means and LS mean difference between etrasimod and placebo) for each MI dataset will be combined and reported along with 95% CI and p-value and using Rubin's method ([REDACTED]).

All subjects are required to have a baseline EASI score upon randomization. In the unlikely event that a subject is missing baseline EASI, the baseline value will be imputed first using the above covariates. The imputation model will be modified as appropriate based on the actual data.

In addition to the primary method for handling missing data and rescue medication use in the FAS, the following sensitivity analyses will be performed using alternative methods and/or in alternative analysis set:

- FAS, MI tipping point analysis

A tipping point analysis (Carpenter and Kenward 2013) will be performed to investigate the robustness of departures from the missing at random (MAR) assumption in the MI model by applying a specified sequence of shift parameters that modify the imputed EASI values, as follows:

- Missing EASI values will be imputed 100 times, following the MI method described above, with adjustment to the imputed EASI by shift

parameter $S_1=0.5$ in both etrasimod groups. A positive adjustment assumes a worsened outcome. The adjusted EASI value will be capped at 72. Imputed percent change in EASI will be derived accordingly. The MNAR statement with the ADJUST option in PROC MI will be used to apply the shift parameter.

- Each of the 100 completed datasets applying the shift parameters will be analyzed using an ANCOVA model as described above. The results from the 100 completed datasets will be combined for inference using PROC MIANALYZE.
- Repeat the above steps, with adjustment by shift parameter $S_2=1.0$ in both etrasimod groups. Repeat the process for the following pre-specified shift parameters: 0.5, 1.0, 1.5, 2.0...71.5, 72
- The shift parameters that result in a reversed study conclusion (i.e., p-value increases from <0.05 to ≥ 0.05) will be indicated.
- mFAS, using OC (observed data regardless of rescue medication uses and without imputation)

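### The model that imputes EASI after rescue leaves out itch and BSA, two of the three named rescue triggers, so missing at random may not hold and rescued subjects may be imputed too well

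*SAP*

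**What the plan says.** **Deletion.** SAP 8.B states: "EASI scores after rescue medication use will be set to missing". On which rescue counts, it adds: "The rescue medications considered for the purposes of efficacy analysis will include topical and systemic corticosteroids used during the DB Treatment Period".

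**Imputation.** Missing EASI up to Week 12, including the deleted scores, is imputed by fully conditional specification (FCS) with predictive mean matching: "100 imputation models will be generated, including treatment, baseline vIGA (3 versus 4), region", then "baseline EASI score, and EASI scores at the previous scheduled visits". EASI is therefore the only post-baseline predictor. A redacted gap follows region here, as at other mentions of that factor in the SAP, so I read it as the region categories. The SAP allows the model to be modified in light of the data but names no further variable.

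**Rescue.** Protocol 6.8.2 leaves rescue to the investigator, on worsening "as evaluated by the investigator (ie, increased EASI or BSA"), "or as reported by the subject (ie, worse itch"). It asks for severity scores immediately before rescue, at an unscheduled visit if needed.

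**Data available.** SAP 8.A derives weekly peak itch from a daily diary, with Day 1 as baseline, and also records office-based peak itch. Total %BSA is a secondary endpoint analysed by visit (SAP 8.D).

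**Sensitivity.** The SAP 8.B tipping-point analysis addresses "departures from the missing at random (MAR) assumption in the MI model". It applies worsening shifts in the two etrasimod arms only. LOCF, worst case carried forward (WCCF), observed-case analyses and a repeat of the imputation in the mFAS (SAP Table 3) are also planned.

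**The concern.** Imputation under missing at random needs the deletion to be unrelated to the unseen Week 12 EASI once the model's variables are given. Here the protocol itself names what leads to deletion, and two of those three causes are absent from the model. Take two subjects in the same arm and stratum with the same EASI history. One is rescued because itch has become severe and the other is not. The model gives the first an imputation learned from subjects like the second. If severe itch foreshadows worse EASI, that imputation is too good.

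Timing can add to this. EASI is scheduled at Weeks 1, 2, 4, 6, 8 and 12 (SAP 4.E). A subject who flares in Weeks 9 to 11 has Week 8 as the last scheduled score, while the diary records itch every day.

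At stake is the primary estimate, and also the EASI-75 sensitivity analysis in SAP 8.C, which reuses the same imputed values.

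**Working it through.** **1. The plan's own figure.** The plan gives no rescue rate and no imputation bias. Its planning figure is the sample size (SAP 4.C): difference 35, SD 41, one-sided 0.025, power 90%, dropout 25%.

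- Normal approximation: n = 2(1.960 + 1.282)² × 41² / 35² = 28.8, so 29 per arm.
- Exact t-test: 30 per arm (power 90.2%); 30 / (1 − 0.25) = 40. The stated figure reproduces.
- Yardstick: SE of a difference with 40 per arm, unadjusted, is 41 × √(2/40) = 9.2 points.

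**2. When missing at random fails.** Let H be the model's variables and A be itch and BSA. Deletion is ignorable given H if rescue depends only on H, or if A adds nothing to the prediction of Week 12 EASI given H. It fails if rescue depends on A and A does add prediction, or if the EASI flare that led to rescue is not among the scores in H.

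**3. How the bias reaches the difference.** With rescued fraction r and mean imputation error b among the rescued (negative means too good):

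arm bias = r × b; bias in (etrasimod − placebo) = r_E × b_E − r_P × b_P.

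The true difference is −35, so a positive result shrinks the effect.

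**4. Simulations.** Rescue rates, trigger rules and the itch/BSA coefficient are assumptions, because the documents give none. Sequential linear regression stands in for FCS with predictive mean matching.

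*Set 1* imputes within arm, with true means −25 and −60 and simulated SD 34 to 36.

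- Rescue triggered by EASI at a scheduled visit, or by itch/BSA with no extra prediction: bias in the difference at most 0.08 point, which is simulation noise.
- Rescue triggered by itch/BSA, with one SD of it adding 10 points to later EASI beyond history:

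| Rescued, placebo / etrasimod | b_P | b_E | r_P × b_P | r_E × b_E | Simulated bias in difference |
|---|---|---|---|---|---|
| 35% / 20% | −4.0 | −4.3 | −1.4 | −0.9 | +0.55 |
| 25% / 25% | −3.9 | −4.3 | −1.0 | −1.1 | −0.11 |
| 20% / 35% | −3.7 | −4.4 | −0.7 | −1.5 | −0.78 |

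At 5 points per SD and 35%/20%, the bias is +0.21. With itch/BSA in the model, the error among the rescued falls to 0.3 or less.

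*Set 2* has SD 41, six visits and itch-triggered rescue after Weeks 4, 6 and 8. One SD of itch raises next-visit EASI by 0.1 to 0.3 SD.

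| Rescued, placebo / etrasimod | Placebo too good by | Effect shrunk by |
|---|---|---|
| 16–17% / 5% | 1.5 to 3.2 | 0.9 to 2.1 |
| 32–33% / 13–14% | 2.9 to 6.4 | 1.5 to 3.4 |
| 28–30% / 18–21% (separate run, itch persistence 0.7) | 2.7 to 6.7 | 0.8 to 1.9 |

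Adding itch leaves at most 0.1 point. With no itch effect, the bias is about zero.

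*Set 3* is a stress case: one prior scheduled visit, with rescue triggered by an unscheduled EASI flare that the model does not see. Rescued subjects are imputed 15 to 28 points too well. The difference shifts by +2.4 to +4.3 at 35%/20%, 0 at 25%/25%, and −2.4 to −4.3 at 20%/35%. Adding the pre-rescue EASI removes it.

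**5. Against the yardstick.** For itch/BSA, 0.8 / 9.2 = 0.09 SE and 3.4 / 9.2 = 0.37 SE. By normal approximation with 30 per arm, power is 91.1% for a difference of 35 and 85.6% for 32.

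**6. Do the planned analyses cover it?** The tipping point leaves placebo at missing at random. The mFAS imputation uses the same model. LOCF and WCCF use EASI alone, although WCCF penalises every arm. Observed-case analyses keep post-rescue scores, which answers a different question. None uses itch or BSA.

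**The case against.** A reader might infer that missing at random fails by design and that the primary result is therefore biased against etrasimod. The documents do not support that. Increased EASI is the first trigger named and its history is in the model, together with treatment, baseline vIGA and region. EASI contains area scores and an excoriation item (protocol 10.3.1), so it already carries part of the BSA and itch signal. No document says how much itch or BSA adds, or which arm is rescued more.

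Other features reduce the problem. Rescue is to be withheld for four weeks where possible, so several EASI scores would usually precede it. A pre-rescue unscheduled score may enter through the visit windows in SAP 5.C, although the window table is not visible in the public copy. WCCF does test whether placebo was treated too kindly. Rescued subjects count as non-responders in the main key secondary analyses. Shifting only etrasimod guards against a false positive, which is the usual worry. The shift is also a fraction of one standard error in a trial without a formal testing strategy.

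All of this stands as a limit on the size and certainty of the point. It does not answer the narrower observation that two stated causes of deletion, measured beforehand, are left out of the model that replaces the deleted values.

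**Conclusion.** The point holds in conditional form. If itch or BSA predicts later EASI beyond EASI history, or the triggering flare falls between scheduled visits, missing at random given the SAP 8.B model does not hold and rescued subjects are likely imputed too well.

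Under the assumed rates, the itch/BSA mechanism moves the treatment difference by under 1 to about 3 points. The direction follows the rescue imbalance: toward no effect with more placebo rescue, away from it with more etrasimod rescue, and about zero when rescue is balanced or itch and BSA add nothing. These sizes rest on assumed rescue rates and coefficients, and on linear imputation as a stand-in. The between-visit figures are a stress case, not an expectation. It is a modest weakness, worth repairing because the data are already collected.

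**What to change.** In SAP 8.B, pre-specify as auxiliary variables in the FCS model:

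- peak itch NRS: the Day 1 diary value or the office-based peak NRS at baseline (the diary baseline is Day 1 alone, so no weekly mean exists there), and the weekly mean diary peak NRS thereafter;
- total %BSA at baseline and at the previous visits.

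Use pre-rescue values only and set post-rescue values to missing, with the same rescue definition as for EASI. If FCS is unstable, limit the auxiliaries to baseline and the last pre-rescue visit. Leave the ANCOVA unchanged and keep the current model as a sensitivity analysis. The text should also say whether an unscheduled pre-rescue EASI enters the model.

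The cost is SAP wording and programming, more predictors with about 40 subjects per arm, and some missing diary weeks, since a weekly mean needs at least three entries. Naming the variables in advance also narrows the present freedom to modify the model on the data. If the change is made after unblinding, it should be labelled ad hoc, as SAP Section 1 requires.
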